5.3.3.5. Supplementary Analysis

As a supplementary analysis, the primary analysis (Section 5.3.3.1) will be repeated for the randomized analysis set, which includes all randomized participants.

5.3.3.6. Estimator (Analysis) for the Supplementary Estimands of the Primary Endpoint

The same estimators used for the primary estimand will be used for the supplemental estimands.

5.4. Secondary Endpoints Analysis

5.4.1. Secondary Endpoints

5.4.1.1. Definition of Endpoints

The following are the secondary endpoints:

- Symptomatic remission at Week 12
- Endoscopic improvement at Week 12
- Clinical response at Week 12
- Clinical remission at Week 24
- Symptomatic remission at Week 24
- Endoscopic improvement at Week 24
- Clinical response at Week 24
- Histologic-endoscopic mucosal improvement at Week 12

They are defined as follows:

Symptomatic remission: Stool frequency subscore of 0 or 1 and not increased from baseline, and rectal bleeding subscore of 0.

Endoscopic improvement: Endoscopy subscore of 0 or 1 with no friability present on the endoscopy.

Clinical response: Decrease from baseline in modified Mayo score by $\ge 30\%$ and ≥ 2 points, with either a ≥ 1 -point decrease from baseline in the rectal bleeding subscore or a rectal bleeding subscore of 0 or 1. This corresponds to the main definition given in Table 11 in Section 5.5.1.1.

Histologic-endoscopic mucosal improvement: Combination of histologic improvement (neutrophil infiltration in <5% of crypts, no crypt destruction, and no erosions, ulcerations or granulation tissue according to the Geboes²⁾ grading system) and endoscopic improvement as defined above.

5.4.1.2. Main Estimands for Secondary Endpoints

Week 12 secondary endpoints

For secondary endpoints at Week 12, the same estimand that is specified for the primary endpoint will be used (except for the "variable attribute"). The variable attributes are given in Table 7 below:

Table 7: Variable Attributes of Secondary Endpoints at Week 12

Endpoint	Variable attribute
Symptomatic	A binary response variable (response/nonresponse) where response is defined as
remission Week 12	achieving a stool frequency subscore of 0 or 1 and not increased from baseline, and a
	rectal bleeding subscore of 0 at Week 12 and none of the ICEs in categories 1 to 4 and 6
	outlined in Table 6 has occurred prior to the Week 12 visit
Endoscopic	A binary response variable (response/nonresponse) where response is defined as
improvement	achieving an endoscopy subscore of 0 or 1 with no friability present on the endoscopy at
Week 12	Week 12, where none of the ICEs in categories 1 to 4 and 6 outlined in Table 6 has
	occurred prior to the Week 12 visit
Clinical response	A binary response variable (response/nonresponse) where response is defined as
Week 12	achieving a decrease from induction baseline in the modified Mayo score by $\ge 30\%$ and ≥ 2
	points, with either a \geq 1-point decrease from baseline in the rectal bleeding subscore or a
	rectal bleeding subscore of 0 or 1 at Week 12, where none of the ICEs in categories 1 to 4
	and 6 outlined in Table 6 has occurred prior to the Week 12 visit
Histologic-	A binary response variable (response/nonresponse) where response is defined as a
endoscopic mucosal	combination of histologic improvement [neutrophil infiltration in <5% of crypts, no crypt
improvement	destruction, and no erosions, ulcerations or granulation tissue according to the Geboes
Week 12	grading system (Appendix 11)] and endoscopic improvement [endoscopy subscore of 0 or
	1 with no friability present] at Week 12, where none of the ICEs in categories 1 to 4 and 6
	outlined in Table 6 has occurred prior to the Week 12 visit

Week 24 Secondary endpoint

The main estimand for Week 24 secondary endpoints is defined as follows:

i) Treatment by Week 24:

• Experimental 1: Guselkumab q4w [Weeks 0, 4, and 8] followed by guselkumab 200 mg SC q4w

- Experimental 2: Guselkumab GCI q4w [Weeks 0, 4, and 8] followed by guselkumab 100 mg SC q8w
- Control: Placebo SC q4w (Weeks 0, 4, 8, 12, 16, 20)
- **ii) Population**: Participants with moderately to severely active ulcerative colitis as defined by the inclusion/exclusion criteria.
- **iii)** Variable (Endpoint): The variable attributes for secondary endpoints at Week 24 are given in Table 8 below

Table 8: Intercurrent Events and Respective Analysis Strategies for Week 24

Endpoint	Variable attribute
Clinical	A binary response variable (response/nonresponse) where response is defined as achieving a
remission at	stool frequency subscore of 0 or 1 and not increased from baseline, a rectal bleeding subscore
Week 24	of 0, and an endoscopy subscore of 0 or 1 with no friability present on the endoscopy at Week
	24, where none of the ICEs in categories 1 to 4 and 6 outlined in Table 6 has occurred prior to
	the Week 24 visit.
Symptomatic	A binary response variable (response/nonresponse) where response is defined as achieving a
remission at	stool frequency subscore of 0 or 1 and not increased from baseline, and a rectal bleeding
Week 24	subscore of 0 at Week 24, and none of the ICEs in categories 1 to 4 and 6 outlined in Table 6
	has occurred prior to the Week 24 visit.
	•
Endoscopic	A binary response variable (response/nonresponse) where response is defined as achieving an
improvement at	endoscopy subscore of 0 or 1 with no friability present on the endoscopy at Week 24, where
Week 24	none of the ICEs in categories 1 to 4 and 6 outlined in Table 6 has occurred prior to the Week
	24 visit.
Clinical response	A binary response variable (response/nonresponse) where response is defined as achieving a
at Week 24	decrease from induction baseline in the modified Mayo score by $\geq 30\%$ and ≥ 2 points, with
at 1100K 2-1	either a ≥ 1 -point decrease from baseline in the rectal bleeding subscore or a rectal bleeding
	subscore of 0 or 1 at Week 24, where none of the ICEs in categories 1 to 4 and 6 outlined in
	Table 6 has occurred prior to the Week 24 visit
Ĭ	

- iv) Intercurrent Events and Corresponding Strategies: ICEs and the corresponding analysis strategies are defined in Table 6.
- v) Population-level summary: Difference in proportions of participants who achieved the binary response at Week 24 as defined in the variable attribute above between each of the guselkumab groups and the placebo group.

5.4.1.3. Supplementary Estimands for Secondary Endpoints

5.4.1.3.1. Treatment policy for discontinuations (Estimand 5)

Supplementary estimands (Estimand 5 for secondary endpoints) handle all treatment discontinuation ICEs, i.e. ICEs 3, 5 and 6 in Table 6, by the treatment policy strategy. ICEs 1, 2 and 4 in Table 6 continue to be handled by the composite strategy. This leads to the variable definitions given in Table 9.

Table 9: Variable Attributes of Secondary Endpoints for supplementary estimand

Endpoint	Variable attribute
Symptomatic remission Week 12	A binary response variable (response/nonresponse) where response is defined as achieving a stool frequency subscore of 0 or 1 and not increased from baseline, and a rectal bleeding subscore of 0 at Week 12 and none of the ICEs in categories 1, 2 and 4 outlined in Table 6 has occurred prior to the Week 12 visit
Endoscopic improvement Week 12	A binary response variable (response/nonresponse) where response is defined as achieving an endoscopy subscore of 0 or 1 with no friability present on the endoscopy at Week 12, where none of the ICEs in categories 1, 2 and 4 outlined in Table 6 has occurred prior to the Week 12 visit
Clinical response Week 12	A binary response variable (response/nonresponse) where response is defined as achieving a decrease from induction baseline in the modified Mayo score by $\geq 30\%$ and ≥ 2 points, with either a ≥ 1 -point decrease from baseline in the rectal bleeding subscore or a rectal bleeding subscore of 0 or 1 at Week 12, where none of the ICEs in categories 1, 2 and 4 outlined in Table 6 has occurred prior to the Week 12 visit
Histologic- endoscopic mucosal improvement Week 12	A binary response variable (response/nonresponse) where response is defined as a combination of histologic improvement [neutrophil infiltration in <5% of crypts, no crypt destruction, and no erosions, ulcerations or granulation tissue according to the Geboes grading system (Appendix 11)] and endoscopic improvement [endoscopy subscore of 0 or 1 with no friability present] at Week 12, where none of the ICEs in categories 1, 2 and 4 outlined in Table 6 has occurred prior to the Week 12 visit
Clinical remission Week 24	A binary response variable (response/nonresponse) where response is defined as achieving a stool frequency subscore of 0 or 1 and not increased from baseline, a rectal bleeding subscore of 0, and an endoscopy subscore of 0 or 1 with no friability present on the endoscopy at Week 24, where none of the ICEs in categories 1, 2 and 4 outlined in Table 6 has occurred prior to the Week 24 visit.
Symptomatic remission Week 24	A binary response variable (response/nonresponse) where response is defined as achieving a stool frequency subscore of 0 or 1 and not increased from baseline, and a rectal bleeding subscore of 0 at Week 24, and none of the ICEs in categories 1, 2 and 4 outlined in Table 6 has occurred prior to the Week 24 visit.
Endoscopic improvement Week 24	A binary response variable (response/nonresponse) where response is defined as achieving an endoscopy subscore of 0 or 1 with no friability present on the endoscopy at Week 24, where none of the ICEs in categories 1, 2 and 4 outlined in Table 6 has occurred prior to the Week 24 visit.
Clinical response Week 24	A binary response variable (response/nonresponse) where response is defined as achieving a decrease from induction baseline in the modified Mayo score by $\geq 30\%$ and ≥ 2 points, with either a ≥ 1 -point decrease from baseline in the rectal bleeding subscore or a rectal bleeding subscore of 0 or 1 at Week 24, where none of the ICEs in categories 1, 2 and 4 outlined in Table 6 has occurred prior to the Week 24 visit.

5.4.1.3.2. Alternative Mayo Score Calculation (Estimand 6)

This supplementary estimand (Estimand 6) follows the main estimand for the secondary endpoints in all attributes. The eligible days to be used for the Mayo scoring for this estimand are all available days among the seven days prior to each visit, excluding programmatically the following two days:

- 3. The day(s) of a procedure (including colonoscopy or sigmoidoscopy)
- 4. The day preceding such a procedure.

This estimand does not apply to endoscopic improvement at Week 12 / Week 24 nor to histologic-endoscopic mucosal improvement at Week 12.

5.4.2. Analysis Methods

5.4.2.1. Main Estimators (Analyses) for the Main Estimands for the Secondary Estimands

The analysis of the secondary endpoints will be based on the Full Analysis Set. Participants will be analyzed according to the treatment group to which they were randomized regardless of the treatment they received. After accounting for the ICE strategies, any missing data for the secondary endpoints will be handled by nonresponder imputation. In particular the following rules will be applied:

- Participants who are missing baseline stool frequency at baseline will be considered as not having achieved clinical remission or symptomatic remission at any timepoint
- Participants who are missing any of the modified Mayo subscores at baseline will be considered as not having achieved clinical response at any timepoint
- Participants who have missing endoscopy subscore at Week 12 will be considered as not having achieved endoscopic improvement or histologic-endoscopic mucosal improvement at Week 12;
- Participants who are missing either the stool frequency or the rectal bleeding subscore at Week 12 or at Week 24 will be considered as not having achieved symptomatic remission at the respective timepoint;
- Participants who are missing any of the modified Mayo subscores at Week 12 or at Week 24 will be considered as not having achieved clinical response at the respective timepoint;
- Participants who are missing any of the modified Mayo subscores at Week 24 will be considered as not having achieved clinical remission at Week 24;
- Participants who are missing any or all of the components in the Geboes grading system pertaining to the histologic improvement at Week 12 will be considered as not having achieved histologic-endoscopic mucosal improvement at Week 12.

Summaries of the proportion of participants achieving each secondary endpoint by treatment group along with the adjusted treatment difference between the combined guselkumab SC induction group (Week 12 endpoints) / individual guselkumab SC induction groups (Week 24 endpoints) and the placebo group, as well as the associated 95% confidence interval will be presented for each secondary endpoint. Each comparison against placebo will be performed in terms of the common (overall) risk difference for multiway 2x2 tables at a two-sided significance level of 0.05. Specifically, the adjusted treatment differences, 95% confidence intervals, and p-values will be in terms of the common risk difference by use of Mantel-Haenszel stratum weights and the Sato variance estimator; stratification is by ADT-IR status (Yes/No), and Mayo endoscopy subscore at baseline (moderate [2] or severe [3]).

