5. Discontinuation of study intervention due to COVID-19 related reasons (excluding COVID-19 infection)	Treatment policy strategy: Observed values will be used if available	
6. Discontinuation of study intervention due to reasons other than ICEs 3 or 5 as described above	Composite strategy: Occurrence of these ICEs will be treated as an unfavorable outcome	

v) Population-level summary: Difference in proportions of participants who achieved the binary response at Week 24 as defined in the variable attribute above between each of the guselkumab groups and the placebo group.

Estimator for Secondary Efficacy Endpoints

The analysis of the secondary endpoints will be based on the Full Analysis Set. Participants will be analyzed according to the treatment group to which they were randomized regardless of the treatment they received.

After accounting for the ICE strategies, any participants who are missing any or all of the components that define the secondary endpoints at Week 12/Week 24 will be considered not to meet the respective endpoint (ie, nonresponder imputation).

Summaries of the proportion of participants achieving each secondary endpoint will be presented by treatment group. The common risk difference and the associated 95% confidence interval between the combined guselkumab SC induction group (Week 12 endpoints) / individual guselkumab SC induction groups (Week 24 endpoints) and the placebo group will be computed by use of Mantel-Haenszel stratum weights and the Sato variance estimator. The secondary endpoints will be tested by a two-sided Mantel-Haenszel test for the common risk difference. Stratification will be by the ADT-IR status (Yes/No), and COL at baseline (moderate [2] or severe [3]) obtained during central review of the screening video endoscopy.

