1.2. Study Design

This is a randomized, double-blind, placebo-controlled, parallel-group, multicenter study to evaluate the efficacy and safety of guselkumab SC induction therapy in adult participants with moderately to severely active UC defined as a modified Mayo score of 5 to 9, inclusive, Mayo rectal bleeding subscore ≥ 1 and a Mayo endoscopy subscore ≥ 2 . Participants must have demonstrated an inadequate response to or intolerance of conventional (i.e., 6-mercaptopurine (6-MP), azathioprine (AZA), or corticosteroids) or advanced therapy (ADT; i.e., tumor necrosis factor (TNF) α antagonists, vedolizumab, ozanimod, or approved Janus kinase (JAK) inhibitors). An overview over the study design is given in Figure 1.

A target of 399 participants will be enrolled in this study with 133 participants planned per intervention group. Participants who had an inadequate response to or intolerance of advanced therapy (ADT-IR) will comprise a minimum of approximately 40% and a maximum of approximately 50% of the population. Consented participants will be screened for study eligibility within 8 weeks of the Week 0 visit. Eligible participants will be randomized in a 1:1:1 ratio to the following intervention groups:

- Guselkumab CCI at Weeks 0, 4, and 8 followed by guselkumab 200 mg SC q4w through Week 24
- Guselkumab CCl at Weeks 0, 4, and 8 followed by guselkumab 100 mg SC q8w through Week 24
- Placebo SC q4w from Week 0 through Week 24

Participants will be allocated to an intervention group using permuted block randomization stratified by ADT-IR status (Yes/No) and Mayo endoscopy subscore at baseline (moderate [2] or severe [3]).

At weeks 12 and 16, all participants will be evaluated according to predefined rescue criteria as given below. All participants in the placebo group who meet rescue criteria at Week 16 will receive rescue treatment, i.e., guselkumab at Weeks 16, 20, and 24 followed by guselkumab 100 mg SC q8w. Participants randomized to guselkumab who meet rescue criteria at Week 16 will continue their assigned treatment regimen and receive blinded sham rescue with matching placebo SC injections at Weeks 16, 20, and 24.

Rescue criteria are defined as:

• No improvement (i.e., no decrease) in Mayo endoscopy subscore at Week 12, when compared with baseline

AND

• A <2 point improvement (i.e., <2 point decrease) in partial Mayo score at Weeks 12 and 16, when compared with baseline

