5.4.2.2. Multiple Testing Procedure

A multiple testing procedure is planned to control the overall Type 1 error rate in the study at the 2-sided 0.05 significance level. The planned procedure is depicted in Figure 2. It follows a fixed sequence approach, where the primary endpoint and the Week 12 secondary endpoints (with the exception of histologic-endoscopic mucosal improvement) for the combined guselkumab groups vs. placebo are tested prior to the secondary endpoints at Week 24. For the Week 24 endpoints, the testing sequence continues with testing all four endpoints in the guselkumab [CC] [Queen q4w [Weeks 0, 4, and 8] followed by guselkumab 200 mg SC q4w group against placebo and then testing all four endpoints in the guselkumab [Queen q4w [Weeks 0, 4, and 8] followed by guselkumab 100 mg SC q8w group against placebo. Histologic-endoscopic mucosal improvement at Week 12 is the last element of the testing sequence and is tested for the combined guselkumab groups against placebo.

[figure not shown]

Figure 2: Multiple Testing Procedure for Primary and Secondary Endpoints

Note: All p-values are two-sided

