- Sustained clinical remission: Clinical remission at Week 12 and Week 24 (Week 24 DBL) and at Week 12, Week 24 and Week 48 (Week 48 DBL)
- Maintenance of clinical remission at Week 24 and at Week 48 among participants achieving clinical remission at Week 12
- Maintenance of clinical remission through Week 48 (at both Week 24 and Week 48) among participants achieving clinical remission at Week 12
- Sustained clinical response: Clinical response at Week 12 and Week 24 (Week 24 DBL), Week 12, Week 24 and Week 48 (Week 48 DBL)
- Symptomatic remission over time among participants achieving symptomatic remission at Week 12 (Week 48 DBL only)
- Durable symptomatic remission through Week 48: Defined as achieving symptomatic remission for >80% of all visits between Week 0 (excluding) and Week 48 (including)

The changes from baseline over time will be evaluated for full Mayo score, modified Mayo score, partial Mayo score, and Mayo stool frequency and rectal bleeding and subscores. The full Mayo score and the modified Mayo scores require an endoscopy and will therefore only be evaluated at Week 12, Week 24 and Week 48. The partial Mayo score will be evaluated at all visits.

The following evaluations for completeness/missingness of the Mayo score will be done at Week 12, Week 24 and Week 48:

- Summary of completeness of modified Mayo score and the full Mayo score
- Number of participants who experienced intercurrent events prior to Week 12, prior to Week 24 and prior to Week 48
- Summary of Mayo subscores through Week 12, through Week 24, and through Week 48
- Summary of missing modified Mayo score and the full Mayo score components after accounting for ICE strategies and by intercurrent event occurrence

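### Clinical response at Weeks 12 and 24 is scored as failure when one modified Mayo subscore is missing, even for the participants whose observed subscores already prove response

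*SAP*

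**What the plan says.** SAP 5.4.1.1 defines clinical response as a "Decrease from baseline in modified Mayo score by" at least 30% and at least 2 points, together with either a drop of at least 1 point in the rectal bleeding subscore or a rectal bleeding subscore of 0 or 1. The endoscopy subscore enters only through the total: SAP 5.5.1.1 notes that "The full Mayo score and the modified Mayo scores require an endoscopy".

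Among the missing-data rules in SAP 5.4.2.1, anyone "missing any of the modified Mayo subscores at Week 12 or at Week 24 will be considered as not having achieved clinical response", judged visit by visit. Protocol 9.4.3.1 says the same in general form: those "missing any or all of the components that define the secondary endpoints at Week 12/Week 24 will be considered not to meet the respective endpoint". Neither document makes an exception.

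The endpoint is confirmatory. The fixed sequence in SAP 5.4.2.2 opens with "the primary endpoint and the Week 12 secondary endpoints (with the exception of histologic-endoscopic mucosal improvement"), so Week 12 clinical response is included. It then takes all four Week 24 endpoints for each regimen against placebo.

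The tipping-point and multiple-imputation analyses in SAP 5.3.3.3 cover only the primary estimand. SAP 5.4.2.3 applies the same estimators to the supplementary estimands of the secondary endpoints, so Estimands 5 and 6 inherit the rule.

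**The concern.** Nonresponder imputation is a convention for outcomes that are unknown. Clinical remission and endoscopic improvement carry their own endoscopy threshold, so neither can be confirmed without an endoscopy. Clinical response can be. If stool frequency and rectal bleeding have fallen far enough, no possible endoscopy value would overturn it. With no composite intercurrent event, such a participant satisfies the variable definition in SAP 5.4.1.2, but the estimator records nonresponse. For these people the estimator departs from its own estimand.

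The plan also treats the same visit in two ways. SAP 5.4.2.1 allows symptomatic remission to be scored without an endoscopy, so one participant can be a success on symptomatic remission and a failure on clinical response from the same data.

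At stake are the reported response rates and the treatment difference for clinical response.

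**Working it through.** **Inputs.** Response definition: SAP 5.4.1.1. Entry limits: SAP 1.2, "a modified Mayo score of 5 to 9, inclusive", with rectal bleeding at least 1 and endoscopy at least 2. Planned rates: 30% vs 60% at Week 12 (SAP Table 2) and 35% vs 70% at Week 24 (SAP Table 3). Sizes: 133 placebo vs 266 combined guselkumab at Week 12; 133 vs 133 at Week 24. Assumption: each of the three subscores runs from 0 to 3, since the scoring table in SAP Appendix 10 is not shown. This fits the baseline ceiling of 9 and the endoscopy category severe [3].

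**1. The plan's power.** A two-sided pooled chi-square test at 0.05 gives 99.996% at Week 12 (stated as >99%) and 99.997% at Week 24 (stated as 99%). Both stated figures are supported.

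**2. When is response proved?** The total rises with the missing subscore, so response is proved if all criteria hold with that subscore set to 3.
- Proved: baseline stool 2, bleeding 2, endoscopy 2 (total 6); follow-up stool 0, bleeding 0, endoscopy missing. The worst total is 0 + 0 + 3 = 3, a fall of 3 points (3/6 = 50%) with bleeding 0. The SAP scores this as failure.
- Not proved: baseline 1, 1, 3 (total 5); follow-up stool 1, bleeding 0. At endoscopy 3 the fall is 1 point, which is not a response. At endoscopy 2 the fall is 2 points (40%), which is.

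**3. Enumeration.** There are 20 eligible baselines and 16 observed pairs, so 320 patterns for each missing subscore:

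| Missing subscore | Proved | Ruled out | Depends on missing value |
|---|---|---|---|
| Endoscopy | 64 | 139 | 117 |
| Stool frequency | 64 | 139 | 117 |
| Rectal bleeding | 0 | 66 | 254 |

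All 20 baselines have at least one proved pattern with endoscopy missing. Of the 37 patterns in symptomatic remission, 34 prove clinical response. These are counts of patterns, not of patients. Rectal bleeding can never be bridged, because a value of 3 fails both bleeding conditions.

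**4. Size with similar missingness.** The documents give no rate for a missing endoscopy with observed symptoms and no composite event. I assume 4%, range 2-6%. A simulation under two assumed baseline mixes, calibrated to the planned rates, puts the proved share of such participants at 49-51% (guselkumab) and 18-20% (placebo) at Week 24, and 38-41% and 15-16% at Week 12.
- Week 24 shrinkage = missing rate × (0.50 − 0.19): 4% × 31 = 1.2 points; 2% gives 0.6 and 6% gives 1.9.
- Week 12 at 4%: between 4% × (38 − 16) = 0.9 and 4% × (41 − 15) = 1.0 points.
- Counts at Week 24: 4% × 133 = 5.3 per arm, of whom about 5.3 × 0.50 = 2.7 guselkumab and 5.3 × 0.19 = 1.0 placebo are proved responders.

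A cruder bound avoids the simulated shares by assuming that 50-100% of true responders with a missing endoscopy are provable. Week 24 shrinkage is then rate × share × 35 points, from 2% × 0.5 × 35 = 0.35 to 6% × 1.0 × 35 = 2.1.

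**5. Against sampling error.** The Week 24 standard error is √(0.70 × 0.30/133 + 0.35 × 0.65/133) = 5.7 points, so 1.2 points is about one fifth of it. At Week 12 it is √(0.60 × 0.40/266 + 0.30 × 0.70/133) = 5.0 points.

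**6. Unequal missingness.** Week 12, with 30% and 60% as complete-data rates (difference 30.0):

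| Missing, placebo / guselkumab | SAP rule | Difference | After fix, half provable | After fix, all provable |
|---|---|---|---|---|
| 5% / 5% | 28.5% vs 57.0% | 28.5 | 29.25 | 30.0 |
| 10% / 5% | 27.0% vs 57.0% | 30.0 | 30.0 | 30.0 |
| 5% / 15% | 28.5% vs 51.0% | 22.5 | 26.3 | 30.0 |
| 15% / 5% | 25.5% vs 57.0% | 31.5 | 30.7 | 30.0 |

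Because the guselkumab rate is twice the placebo rate here, the difference is inflated once placebo missingness exceeds twice guselkumab missingness. Across all scenarios run (2-15% missing, both weeks), the lowest power under the SAP rule is 99.2%.

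**The case against.** The strongest reply is that this is plain, prespecified nonresponder imputation, stated alike in protocol and SAP, and that a bounding rule is only a preference. It is true that the documents do not contradict each other and that no figure is wrong. But the reply covers only the undetermined cases. In the proved ones nothing is being imputed.

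The affected group is narrow, and that stands. A participant must have observed stool and bleeding subscores, no intercurrent event in categories 1-4 or 6, and no endoscopy anywhere in the analysis window. SAP 5.1.1 slots early-discontinuation and unscheduled endoscopies into days 57-113 and 141-197.

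Part of the problem will be visible. SAP 5.5.1.1 summarises missing modified Mayo components after intercurrent-event handling. That shows how much is missing, but not how many of those participants are proved responders.

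A reader might infer that the rule biases the treatment effect downward and is therefore at least conservative. The documents do not support this as a general statement. It needs similar missingness in the arms, and the 15%/5% case above goes the other way. A reader might also infer that everyone with good symptoms and no endoscopy is a misclassified responder. In 117 of the 320 patterns the endoscopy decides, and for those nonresponder imputation remains reasonable.

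**Conclusion.** The point holds in a limited form. The rule misclassifies a subset of participants whose response is certain, in an endpoint tested for confirmation at Week 12 and, for each regimen, at Week 24. No planned sensitivity analysis covers it. The logic rests only on subscores of 0-3.

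The size rests on more: an assumed 2-6% endoscopy-only missing rate, assumed baseline mixes, and planned rates read as complete-data rates. Under these, with similar missingness, the difference shrinks by roughly 1 point. With unequal missingness the sign is open. The planned power claims are not in doubt, and the outcome of the test is very unlikely to change. What is affected is the accuracy of the reported rates and difference.

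**What to change.** Replace the clinical-response bullet in SAP 5.4.2.1 with a rule of this kind. In the absence of an intercurrent event handled by the composite strategy, a participant missing exactly one of the endoscopy or stool frequency subscores at the visit is a clinical responder if all response criteria hold with that subscore set to 3. In every other case, including two or more missing subscores or a missing rectal bleeding subscore, the participant is a non-responder. Align Protocol 9.4.3.1, list the change in SAP Appendix 2, and report the number of such participants by arm and visit.

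Timing decides its status. Protocol 9.4 requires the SAP to be final before the Week 24 database lock, and the documents do not say whether that lock has occurred. If the Week 24 data are already unblinded, keep the prespecified rule as the main analysis and present this one as a labelled sensitivity analysis.

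The cost is a short text change in both documents and a few lines of derivation code. The downside is a slight departure from plain nonresponder imputation, although every undetermined case stays at its worst value.
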